6.13 Adherence of study drug

The dose of study drugs used during treatment period is checked based on the diary. If AE is occurred to the subject, Investigator can reduce or stop the dose of study drugs.

6.14 Unacceptable Concomitant Medication

As explained in the clinical data and pharmacokinetics and pharmacodynamics of Paracetamol, the drugs mentioned below are known to have interactions with Paracetamol. For this reason, it is not acceptable to get the following treatment:

- Opioid Analgesics
- Oral Non Steroid Anti Inflammation Drugs
Caution is recommended when analgesic products are used in combination because of possible increases in adverse events (e.g. nephrotoxicity, gastrointestinal lesions, bleeding).
- Alcohol
- Anticoagulants – Oral, Injection: Piroxicam is highly protein bound. There is therefore a possibility of interaction with such drugs as coumarin anticoagulants

7 STUDY PLAN

7.7.1 Group Composition

The following 2 groups are examined. The participants are allocated to these groups at the ratio of 1:1 that will be randomized.

[figure not shown]
- Test drug group : Piroxicam plus Counterirritant Gel
- Comparator group : Diclofenac diethylamine Gel
- Comparator group : Piroxicam Gel

7.7.2 Study period and process

The study period for each participant is defined as “the period from the day of consent to the end of study (the day on which final tests and observation are finished or the day of discontinuation of the study).

The participants considered as a complete visit after the 3rd visit examination on 6 ± 1 days visit.

[figure not shown]
- 1st visit consider as Day 0
- 2nd visit is on Day 3 ± 1 days
- 3rd visit is on Day 6 ± 1 days

The study's flow in Day 0 :

- 1) The registration officers will receive participants who register at the Eminence clinic and ask about symptoms related to the participant's visit. If the Participant complains of pain, the patient will be asked to fill out a registration form.
- 2) The Principal Investigator or Sub Investigator will ask some questions (anamnesis) about the symptoms and explain about a clinical study that is conducted in the clinic. The PI or Sub-I will ask the Participant's willingness to join the research and explain regarding informed consent. If the Participant agrees, an informed consent will be signed.
- 3) The participants are asked to complete the Individual Assesment of Pain.
 - a. Form 2 : Pemeriksaan Inventerisasi Rasa Nyeri Singkat
- 4) The examination was carried out by conducting anamnesis, physical examination to confirmation the musculoskeletal pain, range of motion and muscle test and confirmation related to the inclusion and exclusion criteria. If needed a radiologic examination will be conducted.
- 5) In the examination, the PI or Sub-I should complete some Forms :
 - a. Form 3 : Pemeriksaan Awal Rasa Nyeri
 - b. Form 4 : Pemeriksaan Indikator Rasa Nyeri Non Verbal
 - c. Form 5 : Pemeriksaan Rentang Gerak
 - d. Form 6 : Pemeriksaan Kekuatan Otot
- 6) The PI or Sub-I will provide a diagnosis and therapy appropriate to the diagnosis.

- 7) Randomization of participants is carried out helped by Study Coordinator. The administration of therapeutic drugs according to the randomization list by a physiotherapist. The physiotherapist will provide information related to how to apply topical drugs to participants and provide the first dose of the investigational product in the therapy room.
 - a. Form 7: Pemberian aplikasi obat topikal by Physiotherapist
 - b. Form 8: Sensasi Termal by Participant
- 8) Each participant will get physical therapy program referred to standard protocol and diagnosis
- 9) Each participant will be given a pouch containing 2 tubes of investigational products, 3 dosing cards, 4 strips of rescue medications, a participant diary, a study coordinator business card and a PI or Sub-I business card.

The study's flow in Day 1 - Day 3 (\pm 1 day)

- 1) Participants will continue topical medication sessions at home. The Study Coordinator will assist with daily reminders for topical medication administration and diary completion. Participants will be asked to return to the study site on day 4 \pm 1 day with carrying the left over tubes and rescue medications, dosing cards, diary and put inside the pouch.
- 2) The participant will do the re-registration to registration officer and send back the pouch that will be given to the Fisiotherapist.
- 3) The examinations will remains same as Day 0 from poin 2 until 5.
- 4) The physiotherapist will provide information related to how to apply topical drugs to participants and applied the dose of the investigational product in the therapy room.
- 5) The administration of therapeutic drugs according to the randomization list by a physiotherapist. The physiotherapist will provide information related to how to apply topical drugs to participants and provide the dose of the investigational product in the therapy room.
 - o Form 7: Pemberian aplikasi obat topikal by Physiotherapist

- Form 8: Sensasi Termal by Participant

- 6) Each participant will be given a pouch containing 2 tubes of investigational products, 3 dosing cards, 4 strips of rescue medications, a participant diary, a study coordinator business card and a PI or Sub-I business card.
- 7) Participants will continue topical medication sessions at home. The Study Coordinator will assist with daily reminders for topical medication administration and diary completion. Participants will be asked to return to the study site on day 8 ± 1 with carrying the left over tubes and rescue medications, dosing cards, diary and put inside the pouch.

The study's flow in Day 5 - Day 6 (± 1 day)

- 1) Participants will continue topical medication sessions at home. The Study Coordinator will assist with daily reminders for topical medication administration and diary completion. Participants will be asked to return to the study site on day 6 ± 1 day with carrying the left over tubes and rescue medications, dosing cards, diary and put inside the pouch.
- 2) The participant will do the re-registration to registration officer and send back the pouch that will be given to the Fisiotherapist.
- 3) The examinations will remains same as Day 0 from poin 2 until 5.
- 4) The PI or Sub-I will give information that this is the last day of the study and the investigational drugs application last dose will be given by the physiotherapist.
- 5) The administration of therapeutic drugs according to the randomization list by a physiotherapist. The physiotherapist will provide information related to how to apply topical drugs to participants and provide the last dose of the investigational product in the therapy room.
 - Form 7: Pemberian aplikasi obat topikal by Physiotherapist
 - Form 8: Sensasi Termal by Participan
- 6) End of Study.

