The selection of difference more than equal to 3 was chosen because if the participant has moderate pain at the beginning of the treatment, then at the end of the treatment there is a decrease in pain to mild pain. This can be seen that the treatment is effective in dealing with musculoskeletal pain.

5.2 Secondary End-Point:

- 1) In data related to safety assessment, the number of participants who experienced adverse events (including serious adverse events) with each symptom present will be recorded and causality of adverse events and serious adverse events assessed with the help of Naranjo's algorithm

Justification:

At the 1st visit, participants will bring home Participant's Diary. Participants need to fill in if they experienced with others symptoms after get the treatment. Also they need to file the rescue medication that they consume during the study timeline. On the 2nd visit and last visit the Investigator will ask about the diary and confirmed the symptoms and medication. When there is safety report, the Investigator will fill in the Safety Form from BPOM RI (Form Kuning MESO) and assess the safety events with the help of Naranjo's algorithm.

The type of symptoms and the number of participants who have symptoms and including side effects will be recorded and become data related to product safety.

- 2) Investigator Assessment on Participants motions, through Range of Motion (ROM) and Muscle test.

Justification:

One of the symptoms that must be assessed when there is musculoskeletal pain is the range of motion and muscle movement to perform an activity. Therefore, an assessment for the examination of the range of motion and muscle strength carried out by the examining doctor is needed to determine the effect of the treatment carried out in the success of performing the activity.

The effectiveness of the treatment will be seen from the progress in the range of motion that can be performed by the participant at the end of the treatment compared to the beginning of the treatment according to scientific standards.

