6.12 Dispensing, Storage, Management, and Collection Procedures

The Study Drug Handling Manual will be provided and completed to ensure the study drugs are prepared, shipped, stored, dispensed, and returned to comply with regulations.

The Investigational Products will be relabelled in Sponsor Technical Operations Plant Site. After the Sponsor ensures the quality of the product, the study drug will be relabeled, which means that this drug is used explicitly for clinical studies.

The sponsor will deliver the study drug from the Technical Operations plant to each research site by courier, where it can monitor the temperature of the study drug delivery below 30°C.

The Study Coordinator from each research site will ensure the storage of study drugs.

During the study, the distribution of study drug participants will be prescribed by the Investigator based on randomization and dispensed to the participants by the Sports Therapist during the recovery program.

Use GraphPad QuickCalcs (<https://www.graphpad.com/quickcalcs/randomize1/>) to generate a random allocation list, ensuring equal numbers for each treatment group:

- Group A: Piroxicam + Counterirritant
- Group B: Piroxicam
- Group C: Diclofenac

Each eligible participant will be assigned a unique subject ID upon enrollment. The study coordinator will match the subject ID to a treatment group based on the pre-generated list. All tubes will be labeled with a sticker displaying only the randomization code to maintain blinding of both participants and investigators. The tube will then be dispensed to the participant according to the assigned code. Only the investigator will have access to the full randomization list.

At the end of the study period, all study drugs will be returned by the participants to each site. This return process will be assisted by each Study Coordinator. An then be sent to Technical Operations for destruction.

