7.9.1 Primary Endpoint

The assessment of primary endpoint will be assessed through form 2, Inventerisasi Rasa Nyeri Singkat on 1st Visit, 2nd Visit and 3rd Visit.

The primary end-point is the difference BPI scale ≥ 3 , from initial scale of pain to the end of treatment will be captured as the primary efficacy endpoint.

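### Read as written, Visits 2 and 3 put a symptom interview, by an investigator who may know the arm, just before the participant self-rates the primary BPI; taking Form 2 first would reduce this avoidable influence

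*Protocol*

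**What the plan says.** Section 7.9.1 names the primary measure and its timing: "The assessment of primary endpoint will be assessed through form 2, Inventerisasi Rasa Nyeri Singkat on 1st Visit, 2nd Visit and 3rd Visit". The participant fills in the form.

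Section 7.7.2 sets the Day 0 order. At point 2, "The Principal Investigator or Sub Investigator will ask some questions (anamnesis) about the symptoms"; the study explanation and consent follow within the same point. At point 3, "The participants are asked to complete the Individual Assesment of Pain", which is Form 2. The examination and the investigator's Forms 3 to 6 come at points 4 and 5, and randomisation at point 7.

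For both Visit 2 and Visit 3 the flow says "The examinations will remains same as Day 0 from poin 2 until 5". Section 5.2 adds: "On the 2nd visit and last visit the Investigator will ask about the diary and confirmed the symptoms and medication". It does not say whether this questioning comes before or after Form 2.

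On who may know the arm, section 5 declares a single-blind design and describes blinding of participants only. Section 6.12 says "Only the investigator will have access to the full randomization list", yet gives the purpose of the tube labels as "to maintain blinding of both participants and investigators". It also has the study coordinator match subject IDs to arms from the list.

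**The concern.** The primary endpoint is a subjective 0–10 self-rating. If the participant talks through symptoms with someone who knows the assigned gel and then scores the pain, tone, emphasis or expectation can move the score. Two properties of this trial make that worth preventing.

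- It is an equivalence trial with a margin of 1.0 point, so a shift of a few tenths is not small against the margin.
- A shift that draws the arms together looks like success, and the collected data could not tell it from true similarity.

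Nothing in the protocol needs the interview to come first at the follow-up visits.

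**Working it through.** **Order of events.** The point rests on sequence and access, so the sections are set side by side.

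1. Day 0: point 2 is the symptom interview, point 3 is Form 2, points 4–5 are the examination and Forms 3–6, and point 7 is randomisation. The baseline score is given before any arm exists, so baseline is not at issue.
2. Visits 2 and 3 repeat points 2 to 5. The consent part of point 2 cannot recur, but the symptom questions can. In numbered order they precede Form 2.
3. The interviewer is the principal or a sub-investigator. Section 6.12 gives the investigator the list and, in the same paragraph, claims that investigators are blinded. Section 5 blinds participants only. The interviewer's blinding therefore cannot be relied on.
4. At Visits 2 and 3 the participant re-registers with the registration officer before any examination, so a moment for Form 2 already exists.

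**Illustrative scale.** The plan states no figure for this influence, so there is none to reproduce. Inputs:

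- SD 1.81 and 54 per arm before dropout (section 6.7, taken as stated)
- margin ±1.0, tested by TOST (section 7.4.2)
- one-sided alpha 0.05, and 0.0167 as the Bonferroni level in section 6.7
- pull *b* = 0.1, 0.2 or 0.3 points: **an assumption, with no source in the documents**

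SE = 1.81 × √(2/54) = 0.348.

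With a true difference of 1.0 and a pull *b* towards zero, the normal approximation gives

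P(declare equivalence) = Φ(b/SE − z) − Φ((b − 2)/SE + z), with z = 1.645 or 2.128.

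| b | b/SE | alpha 0.05 | alpha 0.0167 |
|---|---|---|---|
| 0 | 0 | 5.0% | 1.7% |
| 0.1 | 0.287 | 8.7% | 3.2% |
| 0.2 | 0.574 | 14.2% | 5.9% |
| 0.3 | 0.861 | 21.6% | 10.0% |

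Using the t distribution changes these by about 0.2 percentage points at most.

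The direction can also go the other way. If the arms are truly equal and the influence favours one gel by *b*, then P = Φ((1 − b)/SE − z) − Φ((−1 − b)/SE + z). At alpha 0.05 this falls from 78% at b = 0 to 62% at b = 0.3.

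**The case against.** **The order is loosely drafted.** Point 2 is largely explanation and consent, and point 4, after Form 2, has an anamnesis of its own. Once consent drops out, a site could reasonably hold the follow-up interview at point 4. This stands as a reason to say that the order holds on a plain reading, not that it is firmly fixed. It does not answer the point, because nothing puts Form 2 first.

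**The interviewer's knowledge of the arm is not settled.** A reader might infer that the interviewer certainly holds the list. The documents do not support that: section 6.12 contradicts itself, and it does not say whether the investigator with access includes sub-investigators. What stands is that the interviewer may know.

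**Re-ordering is not a cure.** A reader might infer that moving Form 2 removes the bias. It does not. These routes remain:

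- access to the list itself
- carry-over from the Visit 2 interview to the Visit 3 score
- the coordinator, who matches IDs to arms and sends daily reminders
- the physiotherapist, who applies the gel according to the list
- the C, H and P codes and sticker colours on the tubes (section 6.9)

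**The participant circles the number.** Self-completion gives some protection, but not against suggestion just before the form is filled in.

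**Conclusion.** The point holds as a cheap improvement. On the plain reading of section 7.7.2, the post-baseline primary scores follow an investigator's symptom interview, and section 6.12 leaves open that this investigator knows the arm. The procedure creates an avoidable possibility of influence; the documents offer no evidence that it occurs or how large it would be.

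The percentages should not be read as this trial's error rate. They require a true difference exactly at the margin, an assumed pull in one direction only, and the plan's SD and group size. At the plan's adjusted alpha they are about half of those at 0.05 or less. They show only that a few tenths of a point matter against a margin of 1.0.

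The root defect is the contradiction over list access. The order of Form 2 is still worth fixing once that is resolved, because the design stays single-blind and other cues to the arm remain.

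**What to change.** 1. In section 7.7.2, for Visits 2 and 3, replace the reference back to Day 0 points 2–5 with an explicit order: the participant completes Form 2 alone at re-registration and hands it in there; then come the interview, diary review, examination and Forms 3–6. Drop the literal repeat of point 2.
2. Leave Day 0 as it is. It precedes randomisation, and its symptom questions come before consent, so Form 2 could not be placed ahead of them.
3. In section 6.12, reconcile the statements on list access and investigator blinding, so that whoever interviews and examines participants has no access to the list.

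**Cost.** The order change is a wording change with no effect on sample size, alpha or analysis. There are two small downsides. The registration desk takes on receiving a form, whereas section 7.9 assigns endpoint assessment to the investigators and the physiotherapist. Also, baseline Form 2 would follow symptom questions while later ones would not; this is the same in every arm, so a common shift cancels in the between-arm difference in mean change, although it could slightly move the ≥ 3-point response rates in all arms. Item 3 needs someone outside the interview and examination to hold the list.

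### Section 7.7.2 defines Visits 2 and 3 as Day 3 ± 1 and Day 6 ± 1, but two of its own flow steps recall participants on day 4 ± 1 and day 8 ± 1

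*Protocol*

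**What the plan says.** Section 7.7.2 of the Protocol sets the visit days in a short list. Visit 1 is Day 0. For the other two it states "2nd visit is on Day 3 ± 1 days" and "3rd visit is on Day 6 ± 1 days". The same section ties completion to that last window: "The participants considered as a complete visit after the 3rd visit examination on 6 ± 1 days visit".

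The figure of 6 ± 1 days also stands in the objective (section 4), the design statement (section 5), the three drug sections (6.8.1 to 6.8.3) and the schedule table (7.9). The table repeats Day 3 ± 1 for Visit 2 as well.

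The step-by-step flow in 7.7.2 then gives three recall instructions:

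- Day 1 to Day 3 flow, step 1 (recall for Visit 2): "Participants will be asked to return to the study site on day 4", with a tolerance of one day either side.
- Day 1 to Day 3 flow, step 7 (given at Visit 2, recall for the last visit): "Participants will be asked to return to the study site on day 8 ± 1 with carrying the left over tubes".
- Day 5 to Day 6 flow, step 1 (the same last visit): "Participants will be asked to return to the study site on day 6 ± 1 day with carrying the left over tubes".

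The third agrees with the definition. The first two do not, and the second and third give different days for one visit.

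**The concern.** Visit 3 carries the final BPI score. Section 5.1 takes the primary endpoint as the change from the initial score to the end of treatment, and section 7.4.2 tests equivalence on the mean change from baseline. At the same visit the physiotherapist is to "provide the last dose of the investigational product in the therapy room", so the visit day also fixes the length of treatment.

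Step 7 is the instruction in force when a participant leaves Visit 2 with new tubes and is told when to come back. A site that follows it as written can schedule the final assessment on Day 8 or 9. Two things are then at stake:

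- **Timing of the primary endpoint.** Section 2.2 says that acute musculoskeletal pain usually improves over two or three weeks without treatment. A later final score therefore tends to show more change in every arm, and more participants past the fixed 3-point cut-off.
- **Membership of the primary analysis set.** The Per Protocol Set in section 7.4.1 requires the primary endpoint assessments to be completed as the protocol specifies. For a final score on Day 8 or 9 the protocol specifies two incompatible things, so a participant who came back as instructed could be kept or excluded, with an argument for either.

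**Working it through.** **1. Windows compared.** All days are counted from Visit 1 = Day 0, as 7.7.2 states.

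| Visit | Defined (7.7.2 list, 7.9 table) | Recall step (Day 1 to Day 3 flow) | Shared days | Recall days out of window |
|---|---|---|---|---|
| 2 | 3 ± 1: Days 2, 3, 4 | 4 ± 1: Days 3, 4, 5 | 3, 4 | 5 |
| 3 | 6 ± 1: Days 5, 6, 7 | 8 ± 1: Days 7, 8, 9 | 7 | 8, 9 |

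At Visit 3 the recall target itself, Day 8, is out of window. The nominal time from baseline to final BPI becomes 8 days instead of 6 (8/6 = 1.33, or +33%), and the latest permitted day becomes 9 instead of 7.

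**2. Does a different day count explain it?** If the flow counted Day 0 as day 1, Visit 2 would be 3 + 1 = 4 and Visit 3 would be 6 + 1 = 7. That gives 4 and 7, not 4 and 8. There is also no fourth visit for day 8 to refer to, since the flow ends the study at Visit 3.

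**3. Size of the timing effect (illustrative).** The protocol gives no rate of change in pain, so a slope *b* in BPI points per day is assumed, from 0.1 to 0.5. The upper value is the 3-point fall in section 5.1 spread over 6 days (3/6 = 0.5). The planning SD of 1.81 is from section 6.7.

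- Shift in mean change from a 2-day delay: 2*b*.
- If a share *p* of participants is seen on Day 8 and the rest on Day 6, the added variance is *b*² × 2² × *p*(1 − *p*). At *p* = 0.5, where this is largest, it equals *b*².
- SD with mixing: √(1.81² + *b*²), with 1.81² = 3.2761.
- For fixed power and margin, required n is proportional to the variance.

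| *b* | Mean shift, all arms | SD with mixing | Change in SD | Change in n |
|---|---|---|---|---|
| 0.1 | 0.2 | √3.2861 = 1.813 | +0.2% | +0.3% |
| 0.25 | 0.5 | √3.3386 = 1.827 | +1.0% | +1.9% |
| 0.5 | 1.0 | √3.5261 = 1.878 | +3.7% | +7.6% |

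If every participant follows the same text, *p*(1 − *p*) = 0 and no variance is added.

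**The case against.** The strongest reply is that the governing text is clear. Day 6 ± 1 appears throughout the protocol, and the very next flow block repeats it for the same visit, so a careful site would not be misled. It is true that Day 6 ± 1 governs. But the wrong number sits at the step where the return date is given, and on any day except 7 a site cannot satisfy both instructions.

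A second reply is that the consequence is limited, and this stands. The trial is randomised and the equivalence test uses the difference between arms. A delay shared by all arms leaves the expected difference unchanged. The defined window already allows the final score to vary over two days (Day 5 to Day 7). The upper end of the n range needs both the even split, which is the worst case, and a slope taken from a responder threshold, which is not an expected mean change. The 3-point responder comparison is listed among the secondary analyses in 7.4.2. The Visit 2 mismatch is minor, because it affects one day at an interim visit.

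Three stronger readings are tempting, and the document does not support them:

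- *That the wrong date biases the comparison of arms.* The recall step is the same for every participant, and nothing in it depends on the assigned gel.
- *That the flow blocks leave Day 4 uncovered.* The headings carry a tolerance, for example "The study's flow in Day 5 - Day 6 (± 1 day", and the preceding block has the same tolerance. Day 4 therefore falls within both, and the headings need not copy the columns of 7.9.
- *That the diclofenac amount in 6.8.2 should be fixed at 1 gram as part of the same correction.* That is a separate dosing decision. Section 6.8.2 relies on the product leaflet, under which the amount depends on the painful area, and already requires the dosing card. The conversion of 1 gram to 3 cm is attributed in 6.8.1 to data on the test product.

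**Conclusion.** The contradiction is certain. Section 7.7.2 gives two different days for Visit 2 and two for Visit 3, and neither renumbering nor an extra visit explains it. The Visit 3 conflict matters because that visit supplies the primary endpoint, the last dose and the assessment on which Per Protocol Set membership depends.

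The statistical effect is modest. Under the assumed slope of 0.1 to 0.5 points per day, a 2-day delay moves the mean change by 0.2 to 1.0 point in all arms alike. The rise in required n is 0.3% to 7.6% with a worst-case even split, and falls to nothing if all sites follow the same text. No between-arm bias is shown. The correction is worth making because the text is wrong at an operative step and costs almost nothing to repair, not because the design is unsound.

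**What to change.** In the Day 1 to Day 3 flow of section 7.7.2, change the recall day in step 1 from 4 ± 1 to 3 ± 1, and the recall day in step 7 from 8 ± 1 to 6 ± 1. Both steps then agree with the visit list, the completion rule, the 7.9 table and the last flow block.

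The cost is two numbers in one section. Sample size, number of visits, dosing and analysis do not change.
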